3.2 Secondary Endpoints

- Reduction in the progression to acute respiratory failure [Time Frame: 15 days for primary endpoint].
- Patients with a baseline PaO₂/FiO₂ ≥ 200: progression of respiratory failure is defined by:
 - a. severe gas transfer deficit (PaO₂/FiO₂ < 200);
 - b. persistent respiratory distress while receiving oxygen (persistent marked dyspnea, use of accessory respiratory muscles, paradoxical respiratory movements);
- The rate will be calculated as the proportion of patients who experienced at least one of the events above by day+15 from treatment start.

- Reduction in the progression to acute respiratory failure [Time Frame: 28 days].
- Overall survival and all-cause mortality (day 15, day 28).
- Time to improvement in oxygenation for at least 48 hours. Improvement in oxygenation is defined as an increase in PaO₂/FiO₂ of 50 (or greater) compared to the nadir of PaO₂/FiO₂.
- Number of patients requiring mechanical ventilation, if not on mechanical ventilation at study entry.
- Change in the WHO COVID-19, “8-point ordinal scale” from study entry to day 28 (Table 1). To be assessed on day 3, day 8, day 15, day 28.
- Duration of hospitalization and duration of ICU care.
- Toxicity assessment (including incidence of grade 3-5 hemorrhagic events).
- Change in D-dimer [Time Frame: baseline, study day 3, day 8, day 15, and day 28]. Changes in plasma D-dimer level compared with baseline at enrollment.
- Decrease or Change in IL-6:IL-10 ratios.
- Free-Days- at day 28
 - Oxygen
 - Ventilator
 - Vasopressor
 - ICU
 - Hospitalization

Table 1: WHO Ordinal Scale Ordinal Score

Patient State	Descriptor	Score
Ambulatory	No limitation of activities	1
	Limitations of activities	2
Hospitalized (mild disease)	No oxygen therapy	3
	Oxygen by mask or nasal prongs	4
Hospitalized (severe disease)	Non-invasive ventilation or high-flow oxygen	5
	Intubation and mechanical ventilation	6
	Mechanical ventilation + additional organ support – pressors, RRT, ECMO	7
Dead	Death	8

Exploratory Endpoints

- Soluble E-selectin and P-selectin levels compared with baseline at enrollment.
- Thrombosis free days (clinically defined) at day 28.
- Change in other cytokine levels, endothelial or leukocyte activation (day 1, 15, 28) in IL-6, IL-10, Angiopoietin-2, and TNF-alpha

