4.1 Inclusion Criteria

1. Adults, ages 18-85 years.
2. Willing and able to provide informed consent prior to performing study procedures unless they have a legally authorized representative (LAR).
3. Documented COVID-19 pneumonia: defined as upper respiratory tract specimen (nasopharyngeal swab (NPS) or viral throat swab) positive for COVID-19 and/or imaging at computed tomography scan suggestive of COVID-19 pneumonia.
4. Confirmed coronavirus (SARS-CoV-2) infection admitted to the hospital, enrolled ≤ 48 hours of need for supplemental oxygen.
5. Currently hospitalized requiring supplemental oxygen.
6. Have severe COVID-19 according to the WHO Interim Guidance with confirmation by real-time RT-PCR assay. The enrollment criteria with one of the following: respiratory distress, RR ≥ 30 beats/min; oxygen saturation level less than 93% in resting state; or partial pressure of oxygen (PaO₂)/oxygen concentration (FiO₂) ≤ 300 mmHg.
WHO, Clinical management of severe acute respiratory infection when Novel coronavirus (nCoV) infection is suspected: Interim guidance. [https://www.who.int/publications-detail/clinical-management-of-severe-acute-respiratory-infectionwhen-novel-coronavirus-\(ncov\)-infection-is-suspected](https://www.who.int/publications-detail/clinical-management-of-severe-acute-respiratory-infectionwhen-novel-coronavirus-(ncov)-infection-is-suspected).
7. Willing and able to participate in all required evaluations and procedures.

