6.1.1 Procedures during Study Drug Treatment Visits

If a laboratory parameter has been obtained within 48 hours prior to study enrollment, it does not need to be repeated for study purposes and will be considered the *baseline* value. Following the last day of study, no further “study related” blood tests will be obtained.

Guidelines for monitoring hematologic and coagulation parameters were derived from Thachil, J., et al., *ISTH interim guidance on recognition and management of coagulopathy in COVID-19*. *J Thromb Haemost*, 2020. **18**(5): p. 1023-1026.⁴²

- **Pulmonary Indices:** Pulmonary parameters will be recorded daily for subjects from the time of study entry to cessation of study drug therapy. Pulmonary assessment will include a subject’s current level of supplemental oxygen support (%FiO₂), current modality of support (mechanical ventilation, BiPaP, CPAP, nasal cannula, or none), and the results of any chest radiographs (if performed) that day. For patients that remain hospitalized on day 15 or 28 of study, pulmonary indices will also be made at that time point. Blood gas values will be obtained as clinically indicated. Scoring from the WHO COVID Ordinal Scale (Table 1) will be determined as indicated by study investigators or study coordinators.
- **Hematologic parameters:**
A complete blood count including platelets (CBCP) should be obtained at baseline (study entry), and daily until cessation of study therapy. Additional blood counts may be obtained as clinically indicated.
- **Chemistries:**
Serum chemistries (Electrolytes, BUN, creatinine, liver panel) should be obtained at baseline (study entry), and daily until cessation of study therapy. Additional chemistries should be obtained as clinically indicated.
- **Coagulation Labs:**
D-dimer, Prothrombin time (PT), activated partial thromboplastin time (aPTT), and serum fibrinogen should be obtained at baseline (study entry). Additional D-dimer, PT, and serum fibrinogen testing may be obtained as clinically indicated.
- **Serologic Cytokine Profiles:** Biomarkers will be drawn on day 0-1 pre-study drug administration, days 1-7, day 15, and day 28. These will be used to measure e-selectin levels and are not for safety labs. Due to current hospital understaffing, blood draws will occur as staffing permits. Missed blood draws will not be counted as protocol deviations.

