6.2 Study Schedule of Events

Table 4: Events of the Study

	Baseline	Day 1	Day 2	Day 3	Day 4	Day 5	Day 6	Day 7	Day 8	Day 15	Day 28
Eligibility screen	X										
Informed Consent	X										
Medical history	X										
Physical Exam	X	X	X	X	X	X	X	X			
CBC	X ^a	X	X	X	X	X	X	X			
Chemistries	X ^a	X	X	X	X	X	X	X			
ABG	X ^a										
CXR	X ^b										
Biomarkers ^g	X	X	X	X	X	X	X	X		X	X
D-dimer ^g	X			X					X	X	X
Serum pregnancy test	X ^c										
Pulmonary indices ^d	X	X	X	X	X	X	X	X	X	X	X
Uproleselan		X	X	X	X	X	X	X			
Vital Signs ^e		X	X	X	X	X	X	X			
COVID scale	X			X					X	X	X
AE and follow-up ^f		X	X	X	X	X	X	X	X	X	X

Key: CBC-complete blood count; CXR-chest X ray; ABG-arterial blood gas; BP-blood pressure; HR-heart rate; RR-respiratory rate.

Notes:

- a. Laboratory tests performed within 48 hours prior to study enrollment do not need to be repeated at baseline. CBC should be performed daily (until cessation of study therapy) and should be viewed as standard medical care. Arterial blood gas (ABG) measurements, and chest radiographs should be performed per routine medical care. Venous blood gas may be used when ABG unavailable. Patients should continue to have laboratory tests performed (as indicated above) until cessation of study therapy.
- b. Chest X-Ray (CXR): The CXR does not need to be repeated at baseline, if a CXR was done on admission and revealed bilateral infiltrates.
- c. Pregnancy test: Perform in subjects of child-bearing potential, if not already performed this admission for clinical care reasons.
- d. Pulmonary indices will be recorded daily until cessation of drug therapy, and again at day 8, 15 and 28 (if a patient remains hospitalized at that time). Patients who are discharged prior to day 15 or 28 do not need to have pulmonary indices assessed on day 15 or 28.
- e. Vital signs: heart rate, respiratory rate, blood pressure prior to and upon completion of each infusion.
- f. Adverse Event Reporting and Follow-up: Patients will be assessed for adverse events daily during receipt of study therapy, and for 7 days following completion of study drug therapy, provided they remain hospitalized during this 7-day post-therapy period. In addition, patients will be contacted on day 15 and 28 (± 2 days), to assess their clinical status and any active adverse events at that time. This final assessment can be done virtually, by telephone or electronically (email) if the patient cannot be contacted by phone. No in-person visit is required.

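### The day-15 progression endpoint can count respiratory distress already present at entry, because component (b) need not be new or worse after the first dose

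*Combined protocol and SAP*

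**What the plan says.** Section 3.2 lists progression by day 15 first among the secondary endpoints. Its population line reads "Patients with a baseline PaO₂/FiO₂ ≥ 200: progression of respiratory failure is defined by", followed by two events: (a) a ratio below 200, and (b) "persistent respiratory distress while receiving oxygen (persistent marked dyspnea, use of accessory respiratory muscles, paradoxical respiratory movements". The counting rule is "The rate will be calculated as the proportion of patients who experienced at least one of the events above by day+15 from treatment start". Sections 5.2.1, 7.2, 12.1.3 and 12.3 repeat the definition without adding a condition.

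On entry, inclusion 5 in Section 4.1 requires "Currently hospitalized requiring supplemental oxygen". Inclusion 6 begins its list of alternatives with "The enrollment criteria with one of the following: respiratory distress, RR ≥ 30 beats/min", then gives low resting saturation or a PaO2/FiO2 of 300 or less.

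On the baseline gas, Section 6.1.1 states "If a laboratory parameter has been obtained within 48 hours prior to study enrollment, it does not need to be repeated for study purposes" and goes on to make that value the baseline. Note a to Table 4 in Section 6.2, which is attached to the baseline ABG, says "Laboratory tests performed within 48 hours prior to study enrollment do not need to be repeated at baseline". Later blood gases are drawn only as clinically indicated.

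**The concern.** The secondary objective asks whether the drug reduces progression from the state in which patients enter. To measure that, an event has to mark a change from entry. Component (a) has some protection, because the population line removes patients whose baseline ratio is already below 200. Component (b) has none: the ratio screen says nothing about dyspnea or accessory-muscle use, and the counting rule sets a latest date but no condition of onset or worsening.

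The rate would then mix true progression with severity at entry. It is the only outcome given under Section 7.2, Efficacy, and Section 12.2 says the study is meant to contribute to the design of later studies. If the rate is set against the retrospective matched controls, counting entry distress in both groups shrinks any real difference, and an imbalance in entry distress creates a false one.

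The problem may not be repairable at analysis. The daily pulmonary indices in Section 6.1.1 list FiO2, support modality and radiograph results, but not dyspnea or work of breathing. Unless distress is recorded at baseline, new and existing distress may not be separable.

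**Working it through.** The plan states no expected rate, test or power for this endpoint, so there is no figure to reproduce. The check compares the definitions and then does short arithmetic.

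**1. Can an unchanged patient meet (b)?** Take a patient on nasal oxygen with a baseline ratio of 250 who enters in marked dyspnea with accessory-muscle use.
- Inclusion 5: met (on oxygen).
- Inclusion 6: met, through the ratio of 300 or less, and through the distress limb if the respiratory rate also qualifies.
- Population line (ratio at least 200): met.
- Component (b): the same signs, on oxygen, still present after dosing. The term for persistence has no stated duration.
- Counting rule (by day 15 from treatment start): met.

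Nothing in the five sections removes this patient. A patient who qualifies only through saturation or the ratio, without distress, does not meet (b) at entry.

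**2. Weight of one such patient.** Treated N = 15 (Section 12.1). Each patient counted only because of the entry state adds 1/15 = 6.7 points. If the denominator is restricted to patients with a ratio of at least 200, the weight is larger. With 10 such patients (an assumption), it is 1/10 = 10 points.

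**3. Effect on a comparison (illustration only).** Let q be the share counted because of entry distress, equal in both groups, and p the rate of true new progression in the rest.
- Observed rate = q + (1 − q)p, so the difference between groups shrinks by the factor (1 − q).
- Assume p = 40% in controls and 20% in treated patients.

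| q | Control | Treated | Difference |
|---|---|---|---|
| 0 | 40% | 20% | 20 points |
| 3/15 | 0.20 + 0.80 × 0.40 = 52% | 0.20 + 0.80 × 0.20 = 36% | 16 points |
| 5/15 | 0.333 + 0.667 × 0.40 = 60% | 0.333 + 0.667 × 0.20 = 47% | 13 points |

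Neither q nor p is in the documents. The table also takes the extreme case in which all entry distress counts in both groups.

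**4. Age of the baseline gas.** Enrollment may fall 0 to 48 h after oxygen need begins (inclusion 4), and the gas may be up to 48 h older than enrollment. If oxygen need began h hours before enrollment, the gas may predate it by up to 48 − h hours: 48 h at h = 0, 24 h at h = 24, and 0 h at h = 48. Section 5.1 allows the first dose up to 48 h after oxygen need, so at h = 0 the gas could be 48 + 48 = 96 h old at dose 1.

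On room air (FiO2 0.21), a ratio of 200 needs a PaO2 of only 200 × 0.21 = 42 mmHg. With assumed values, a gas before oxygen of 65/0.21 = 310 and one on oxygen before dose 1 of 90/0.50 = 180 put the same patient on opposite sides of the threshold. The patient is wrongly counted only if the 310 is kept as baseline and a further gas after dosing is below 200.

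**The case against.** The strongest reply is that the entry criterion and the event are not the same state. Inclusion 6 names distress with a respiratory rate of 30 or more, which may be one combined limb. Component (b) describes distress that continues despite oxygen, with marked dyspnea, accessory-muscle use and paradoxical movements. This stands, and it limits the problem to patients who enter with signs of that kind. A reader might infer that anyone admitted through the distress limb is an automatic event; the text does not support that.

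Second, calling the endpoint progression and counting from treatment start suggests that events after dosing were intended. That is a fair reading of intent, but no rule puts it into effect, and two assessors could code the same patient differently.

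Third, a reader might infer that the rate rises with entry distress whatever the drug does. That goes too far: distress that resolves soon after dosing need not be called persistent, so treatment can still influence (b).

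Fourth, on the gas, Section 6.1.1 excuses repetition but does not say that an older value overrides a later one obtained before dosing. Section 6.1 ties screening procedures to 48 hours of the oxygen requirement and names only hematology, chemistry and coagulation for use from admission. The documents do not show how often a gas from before oxygen need would exist. This limb is therefore secondary.

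Finally, safety is the primary endpoint, the study is an unpowered pilot, and the progression rate is a descriptive proportion with no test or stopping consequence. Controls are to be of similar severity, which may partly balance entry state. Ventilation, ordinal-scale change and survival are reported separately. This lowers the priority but does not close the gap.

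**Conclusion.** The gap in component (b) is established by the wording: an unchanged entry state can be counted as progression, and no section prevents it. The gap in the baseline gas is real but narrower, since it needs an old gas to be kept as baseline and a low gas after dosing.

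The size cannot be computed from the documents. What can be said is that each patient counted only because of entry distress adds at least 6.7 points, given 15 treated patients, and more if the denominator is restricted to a ratio of 200 or above. A reader might assume that 3 to 5 of 15 enter in such distress and conclude that 20 to 33 points of the rate are spurious. That count has no source in the plan, and the definition does not cover all 15 unless all have a ratio of at least 200. This should be fixed, but for a descriptive secondary endpoint in a safety pilot it does not put the trial's main purpose at risk.

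**What to change.** Make the same change in Sections 3.2, 5.2.1, 7.2, 12.1.3 and 12.3.

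1. Count component (b) only if it was absent at the baseline examination before the first dose, or is documented after the first dose as worse than at baseline. Worsening could be shown by escalation of the oxygen-support modality, already recorded daily during treatment, or by a higher WHO score at the scheduled days thereafter.
2. Define baseline PaO2/FiO2 as the last available value before the first dose, preferring one taken after oxygen was started. No added arterial sampling is needed.

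The cost is wording in five sections and one baseline CRF item recording whether the signs in (b) are present. Some patients will have only an earlier gas; they should be flagged. The WHO scale is scored only at baseline and days 3, 8, 15 and 28, so worsening that comes and goes between visits after treatment ends could be missed.

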4. SUBJECT ELIGIBILITY

Patients with confirmed severe COVID-19 pneumonia admitted to hospital, requiring supplemental oxygen. Subjects must meet all of the inclusion and none of the exclusion criteria to be enrolled in the study. Study treatment may not begin until a subject is enrolled.

4.1 Inclusion Criteria

1. Adults, ages 18-85 years.
2. Willing and able to provide informed consent prior to performing study procedures unless they have a legally authorized representative (LAR).
3. Documented COVID-19 pneumonia: defined as upper respiratory tract specimen (nasopharyngeal swab (NPS) or viral throat swab) positive for COVID-19 and/or imaging at computed tomography scan suggestive of COVID-19 pneumonia.
4. Confirmed coronavirus (SARS-CoV-2) infection admitted to the hospital, enrolled ≤ 48 hours of need for supplemental oxygen.
5. Currently hospitalized requiring supplemental oxygen.
6. Have severe COVID-19 according to the WHO Interim Guidance with confirmation by real-time RT-PCR assay. The enrollment criteria with one of the following: respiratory distress, RR ≥ 30 beats/min; oxygen saturation level less than 93% in resting state; or partial pressure of oxygen (PaO₂)/oxygen concentration (FiO₂) ≤ 300 mmHg.
WHO, Clinical management of severe acute respiratory infection when Novel coronavirus (nCoV) infection is suspected: Interim guidance. [https://www.who.int/publications-detail/clinical-management-of-severe-acute-respiratory-infectionwhen-novel-coronavirus-\(ncov\)-infection-is-suspected](https://www.who.int/publications-detail/clinical-management-of-severe-acute-respiratory-infectionwhen-novel-coronavirus-(ncov)-infection-is-suspected).
7. Willing and able to participate in all required evaluations and procedures.

4.2 Exclusion Criteria

1. In the opinion of at least one investigator, unlikely to survive for >48 hours from screening.
2. Severe chronic respiratory disease (e.g. COPD or other) requiring supplemental oxygen and/or having required mechanical ventilation pre-COVID-19 infection.
3. Concurrent enrollment in a COVID related interventional drug trial. Use of remdesivir, steroids, and convalescent plasma are permitted along with other standard of care therapies for COVID.³⁷
4. Currently on invasive mechanical ventilation.
5. Hypotension defined as systolic blood pressure < 90 mmHg on two sequential readings at least 4 hours apart.
6. Total Bilirubin ≥ 3 x upper limit of normal (ULN), Creatinine Clearance ≤ 30 mL/min/1.73m².
7. Pregnant or breastfeeding.
8. Known diagnosis of an acute thrombosis on admission.
9. Concurrent dual antithrombotic therapy (aspirin or P2Y₁₂ inhibitor plus anticoagulation to treat deep venous thrombosis or pulmonary embolism (single antiplatelet or anticoagulant agent at prophylactic dose is permitted).
10. Concomitant use of thrombolytic therapy.
11. Concomitant therapeutic systemic anticoagulant therapy (e.g. heparin, warfarin, direct thrombin inhibitors and direct factor Xa inhibitors). As per NIH Guidelines: Hospitalized adults with COVID-19 should receive VTE prophylaxis per the standard of care for other hospitalized adults (AIII). Anticoagulant or antiplatelet therapy should not be used to prevent arterial thrombosis outside of the usual standard of care for patients without COVID-19 (AIII); <https://www.covid19treatmentguidelines.nih.gov/therapeutic-management/>
12. History of recent major bleeding, defined in accordance with the criteria of the International Society on Thrombosis and Hemostasis (ISTH).
13. History of bleeding disorder thought to impose excessive bleeding risk as per investigator discretion
14. Hemodynamic instability, defined as inability to maintain mean arterial pressure.
15. Hypersensitivity to the active substance or to any of the excipients of uproleselan.
16. Any physical examination findings and/or history of any illness that, in the opinion of the investigator, might confound the results of the study or pose an additional risk to the patient by their participation in the study

5. SUBJECT SCREENING AND ENROLLMENT PROCEDURES

Patients who present to the University of Michigan Health System who have **confirmed severe COVID-19 pneumonia admitted to hospital, requiring supplemental oxygen** will be recruited. The study research team will contact the potential subject to discuss the study in detail and review the informed consent document. Prior to any study-specific screening evaluations and clinical trial participation, written informed consent will be obtained from each potential subject or legally authorized representative (LAR) in the clinical trial using the Institutional Review Board (IRB) approved informed consent form (ICF). Potential subjects will be informed in detail about the study products to be administered, and the nature of the clinical investigation. The subjects will also be informed that they are free to withdraw their consent and discontinue their participation in the clinical trial at any time. Each subject will be given a copy of the signed ICF.

5.1 Treatment Dosage and Administration

Protocol treatment must start within 48 hours of the admitted patient requiring supplemental oxygen for documented COVID-19 pneumonia. Study enrollment is defined as the day subject meets all of the inclusion criteria and none of the exclusion criteria.

5.1.1 Treatment Plan

Up to 15 subjects will be enrolled in this prospective, interventional, single-arm, open label trial. All drug administration will be performed by nurses in the inpatient unit. Uproleselan injection is a sterile solution for IV administration, supplied in single-dose vials at a concentration of 50 mg/mL. Uproleselan should be administered intravenously (IV) into a peripheral line, a central catheter, or a peripherally inserted central line catheter (PICC). Infusion should take place at a steady rate over a period of 20 minutes \pm 2 minutes using a syringe pump or IV pump. Microbore tubing is preferred. In-line filtration is highly recommended. Dilution of uproleselan may be performed with normal saline (0.9% Sodium Chloride) up to 5x as needed for ease of administration and per institutional practice. Compatibility with other therapeutic agents has not been determined, therefore uproleselan should not be administered concurrently with anything other than saline. When flush is used, saline flush is preferred.

Table 2: Description of Treatment

Agent	Premedications/ Precautions	Dose	Route	Schedule
Uproleselan (GMI-1271)	None	20 mg/kg BID, up to a maximum dose of 2500 mg	IV infusion over 20 min	Daily on treatment days 1-7

Table 3: Standard of Care Treatments

1. Supplemental oxygen, escalate to heated high flow nasal cannula, noninvasive ventilation, endotracheal intubation and mechanical ventilation as needed.
2. Conservative fluid management strategy.
3. Dexamethasone 6mg (PO or IV) qD for up to 10d (RECOVERY trial, Horby PW et al.³⁸
4. Remdesivir 200 mg loading dose, then 100 mg daily for up to 9 additional days (ACTT-1 Study, Beigel JH et al.).³⁹
5. Convalescent plasma for compassionate use.
6. Other medical management as recommended by Infectious Disease Consultants.
7. Management of septic shock.
8. ICU admission as required.

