5.4 Duration of Therapy

Each subject in the treatment arm will receive one dose of uproleselan every 12 hours (12 hours apart optimally; acceptable range 10-14 hours) on treatment days 1-7.

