Life-threatening is defined as an adverse event or suspected adverse reaction in the view of either the investigator or sponsor, its occurrence places the patient or subject at immediate risk of death. It does not include an adverse event or suspected adverse reaction that, had it occurred in a more severe form, might have caused death.

Note that hospitalizations for the following reasons should not be reported as SAEs:

- Previously planned (prior to signing the informed consent form) surgeries should not be reported as SAEs unless the underlying medical condition has worsened during the course of the study.
- Preplanned hospitalizations or procedures for preexisting conditions that are already recorded in the subject's medical history at the time of signing informed consent form should not be considered SAEs.
- Hospitalization or prolongation of hospitalization without a precipitating clinical AE (for example, for the administration of study therapy or other protocol-required procedure)

should not be considered SAEs. However, if the preexisting condition worsened during the course of the study it should be reported as an SAE.

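### Inpatient-only dosing on days 1-7 puts a conditional floor of about 7 days under length of stay for treated subjects, which the matched controls do not share

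*Combined protocol and SAP*

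**What the plan says.** Sections 5.1.1 and 5.2 both place dosing in hospital: "All drug administration will be performed by nurses in the inpatient unit". No outpatient dosing is described. Section 5.4 adds: "Each subject in the treatment arm will receive one dose of uproleselan every 12 hours", with the spacing and days given as "12 hours apart optimally; acceptable range 10-14 hours) on treatment days 1-7".

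The secondary endpoints (Section 3.2, repeated in 5.2.1 and 12.1.3) include "Duration of hospitalization and duration of ICU care", a set of "Free-Days- at day 28" measures of which hospitalization is one, and the WHO 8-point scale, "To be assessed on day 3, day 8, day 15, day 28". On that scale scores 1 and 2 are ambulatory. The best score for an inpatient is 3, the lower of the two categories under "Hospitalized (mild disease").

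The controls (Synopsis, Control row) are matched retrospective patients on best available therapy. No minimum stay or fixed inpatient course is stated for them.

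On discharge before Day 7 the documents are silent. Discharge is not among the listed off-study reasons in Section 5.6. Section 5.7 replaces subjects who are removed.

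**The concern.** Duration of hospitalization and hospitalization-free days are meant to reflect recovery. If a recovered subject stays only to finish the infusions, those days count as illness. This affects the subjects who recover fastest, and only in the treated group, so a comparison of actual stay with the matched cohort would run against uproleselan. Even read within the treated group alone, the values would partly describe the dosing calendar, and Section 12.2 intends the pilot to inform the design of later studies.

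If early recoverers instead go home and stop dosing, the floor disappears but another problem may replace it. Should they count as removed, Section 5.7 replaces them, and the remaining group is selected for longer stays.

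**Working it through.** The plan states no figure on this point, so there is none to reproduce.

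**Schedule arithmetic (inputs: Sections 5.1.1, 5.4, 3.2)**
- Doses: 7 days × 2 = 14, hence 13 intervals.
- First to last dose: 13 × 12 h = 156 h = 6.5 days. At the allowed limits, 13 × 10 h = 130 h = 5.4 days and 13 × 14 h = 182 h = 7.6 days.
- A subject in hospital through Day 7 has at most 28 − 7 = 21 hospitalization-free days. Leaving a day earlier or later gives 22 or 20.
- WHO score, Day 3: this lies inside the dosing window, so the best possible score is 3. Eligibility requires supplemental oxygen and excludes invasive ventilation, so entry scores are 4 or 5. A subject entering at 4 can improve by at most 1 point by Day 3.
- WHO score, Day 8 and later: the last treatment day is Day 7, so these scores are not formally bound.

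**Possible size (assumed inputs)**

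The documents give no length of stay. Let T be the stay from first dose that would occur without the dosing requirement. If every subject with T < 7 is kept to Day 7, the added mean stay is E[(7 − T)+].

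- Log-normal T with median m and log-SD s: E[(7 − T)+] = 7Φ(d) − m·exp(s²/2)·Φ(d − s), where d = ln(7/m)/s. The proportion affected is Φ(d).
- Exponential T with rate r = ln 2/m: E[(7 − T)+] = 7 − (1 − e^(−7r))/r.

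| Assumed median stay | Log-normal, s = 0.5 to 0.8: added days | Log-normal: proportion with T < 7 |
|---|---|---|
| 4 days | 2.8 | 76-87% |
| 5 days | 2.0-2.2 | 66-75% |
| 7 days | 1.1-1.5 | 50% |
| 10 days | 0.4-0.8 | 24-33% |
| 14 days | 0.1-0.4 | 8-19% |

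The exponential form gives 2.9, 2.2 and 1.5 added days at medians of 4, 6 and 10 days. In the log-normal runs, hospitalization-free days fall by the same amount as mean stay rises.

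In the mildest case (median 14, s = 0.5) the proportion affected is 0.0828. The chance that at least one of 15 treated subjects is affected is then 1 − (1 − 0.0828)^15 = 0.73. It is higher in every other case in the table.

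Discharge before Day 3 would be less common: about 0-15% for log-normal medians of 7 to 14 days. The limit on the Day 3 score therefore matters less than the limit on stay.

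**Endpoints not directly affected**

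Oxygen-, ventilator-, vasopressor- and ICU-free days, survival, and the primary safety endpoint do not depend on whether the subject occupies a ward bed for dosing.

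**The case against.** The strongest reply is that the floor is inferred. No section says that a subject fit for discharge is kept for infusions. Section 6.1.1 and note a to Table 4 run laboratory tests until study therapy ceases, not to Day 7. Note g makes study blood draws, including those on days 1-7, conditional on the patient still being in hospital. Section 5.6 lets the investigator withdraw a subject. A shorter course is therefore possible. This stands, and it is why the floor and the cap apply only to a subject dosed to schedule.

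A reader might take Section 8.2.2 as proof that stays will be prolonged for dosing. It excludes from SAE reporting "Hospitalization or prolongation of hospitalization without a precipitating clinical AE (for example, for the administration of study therapy or other protocol-required procedure"). That is general SAE wording. It allows for the situation but does not show that this trial plans it.

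A reader might also extend the floor to the Day 8 WHO score. No dose is scheduled on Day 8, so the documents do not support that.

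Nor is a planned comparison shown to be biased. The Synopsis spells out a contrast with controls only for biomarkers. Section 12.3 gives no method for these endpoints and ranks Day 28 survival and ventilator-free survival as two of the most important. The bias arises if stay is compared with the matched cohort, which the design makes natural but does not prescribe. It would run against the drug, so it would not by itself create a false signal of benefit.

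Finally, the sizes rest wholly on assumed stays and ignore death. An exponential stay with a median of 4 days implies many very early discharges, which is hard to credit in severe disease. Controls may also stay for standard treatments such as remdesivir, but those courses are written with an upper limit, not a fixed length, and are open to both groups.

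**Conclusion.** The point holds in conditional form. Followed as written, Sections 5.1.1, 5.2 and 5.4 keep a fully dosed subject in hospital for about 7 days. This limits hospitalization-free days to about 21 and the Day 3 WHO score to 3 at best. Controls have no such stated limit, so a comparison on actual stay is biased against uproleselan. If early recoverers stop dosing and are replaced, the bias takes the form of selection for longer stays.

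The size cannot be fixed from the documents. The range of about 0.1 to 3 days in mean stay assumes median stays of 4 to 14 days and that every early recoverer is held to Day 7. The documents do not support a claim that all treated subjects will be held, that later WHO scores are bound, or that the main survival summaries or the safety endpoint are compromised.

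**What to change.** - For any comparison of recovery with the control cohort, use time from first dose (a matched index day in controls) to the first day alive and off supplemental oxygen, or the oxygen-free days already listed. Define the measure identically in both groups.
- Report actual duration of hospitalization and hospitalization-free days descriptively. Add the number of treated subjects who were off oxygen but still in hospital during days 1-7.
- Leave WHO scoring unchanged, but do not interpret the Day 3 score against controls without stating that treated subjects dosed to schedule cannot score below 3.
- Reconcile Sections 5.1.1, 5.4, 5.6, 5.7 and 8.2.2 on a subject who is fit for discharge before Day 7, including whether that subject counts as removed and is replaced. The clinical rule is for the sponsor to decide.

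The cost is endpoint wording and one extra derived date per patient, in both groups. The downside is that actual length of stay no longer serves as a comparative efficacy measure. Sample size and treatment need not change.
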